3.4 Expected duration of subject participation

Each subject is planned to participate in the study for up to 2 Visits (Screening and Treatment) and a Follow-up Phone Call 1-4 days following Visit 2 (Day 2-5). A subset of up to 18 subjects will undergo specular microscopy prior to dosing, and approximately 90 days after dosing. The total duration a subject can expect to be in the study is between 2-8 days. If they are in the specular microscopy group, they can expect to be in the study 85-99 days.

3.5 Randomization and procedure for breaking the code

A randomization code for allocating the treatments will be prepared by an independent biostatistician, who is not involved in the day-to-day conduct of the study. Subjects will be randomized in a 2:1 ratio to receive AG-920 or Placebo.

[REDACTED]

If there is an emergency situation in which treatment of an adverse event requires immediate decoding, and the Investigator is unable to contact the Sponsor Safety Officer, the Investigator should treat the subject as if they received active treatment (AG-920) and not placebo. The Investigator should contact the Sponsor immediately and document the AE.

3.6 Participant and Study completion

3.6.1 Completed subject

A completed subject is defined as one who completes all Visits (1 and 2) and the Follow Up Phone call. For those subjects participating in the specular microscopy group, they will not be considered completed until they have had their specular microscopy visit 90 ± 5 days following treatment (Visit 3).

3.6.2 Non-completing subject/Subject Withdrawal

A non-completing subject is defined as one who exits the study by their own volition or at the discretion of the Investigator and/or the Medical Monitor. Any subject may decide to voluntarily withdraw from the study at any time without prejudice and the reason will be documented. In the event that discontinuation of treatment is necessary, the Investigator will make every attempt to complete all subsequent safety assessments. Every attempt should be made to keep subjects in the study and to perform the required study procedures, but if this is not possible, the subject may be withdrawn.

All reasonable efforts should be made to contact the subject who is lost to follow-up. These efforts must be documented in the subject's records.

Subjects may be withdrawn from the study for any reason at any time, including but not limited to the following reasons:

- Subject request
- Use of prohibited concomitant medication/therapy
- Lost to follow-up
- Occurrence of AEs that are not compatible with the continuation of the subject in the study, in the Investigator's opinion, or that make it unacceptable to the subject to continue
- Investigator judgment
- Sponsor request
- Randomization code broken prematurely
- Pregnancy

The reason for early discontinuation will be collected

3.6.3 Discontinuation of the Study

If the clinical study is prematurely terminated or suspended, the Sponsor or designee will inform the Investigators and the regulatory authorities of the termination/suspension and the reason(s) for the termination/suspension. The Investigators should promptly notify their Independent Ethics Committee (IEC) or Institutional Review Board (IRB) of the termination or suspension and of the reasons.

3.6.4 Discontinuation of a Clinical Site

The Sponsor reserves the right to close an investigational site or terminate the study in its entirety at any time, for reasonable cause. Reasons for the closure of any investigational site or termination of the study may include:

- Failure to accrue subjects into the study at an acceptable rate.
- Failure of the Investigator to comply with applicable regulations and Good Clinical Practice (GCP) guidelines.
- Submission of knowingly false information from the research facility to the Sponsor, Food and Drug Administration (FDA), or other regulatory authorities.
- Insufficient adherence to protocol requirements and procedures.

If the study is prematurely discontinued, all study data must be returned to the Sponsor or designee. Additionally, the site must conduct final disposition of all unused IMP in accordance with CRO procedures. Study termination and follow-up will be performed in compliance with the conditions set forth in regulatory guidelines.

Financial compensation to the Investigator and/or institution will be in accordance with the agreement established between the Investigator and the Sponsor or Sponsor designee.

3.6.5 Actions after discontinuation

All subjects who discontinue IMP due to a report of an AE **must** be followed-up and provided appropriate medical care until their signs and symptoms have remitted, stabilized, determined to be chronic, or until abnormal laboratory findings have returned to acceptable or pre-study limits.

For the subject who chooses to withdraw consent or who is non-compliant, every possible effort should be made by the Investigator to assure there is a final visit that includes all examinations listed for Visit 2.

For the subset of subjects participating in the specular microscopy who choose to withdraw consent or who is non-compliant, every possible effort should be made by the Investigator to assure there is a final visit that includes all examinations listed for Visit 3.

3.6.6 Completed study

The end of the study is defined as the date the last subject completes the specular microscopy visit (Visit 3).

3.6.7 Procedure after the completion of the study

When the study is completed and the site has been closed out, the Investigator will be asked to notify the governing IRB.

4 SUBJECT INCLUSION AND EXCLUSION CRITERIA

Subjects must meet all of the following inclusion criteria to be eligible for participation in this study. On criteria that involves the eyes, both eyes must qualify.

4.1 *Subject inclusion criteria*

1. Have provided written informed consent prior to any study-related procedures being performed.
2. Is male or a non-pregnant, non-lactating female aged 18 years or older.
Female subjects of childbearing potential must have a negative urine pregnancy test at Screening (Visit 1) to be eligible for randomization.
3. Are healthy by clinical assessment (detailed medical history), including ocular examination, based on the judgement of the Investigator.
4. [REDACTED]
5. [REDACTED]
6. [REDACTED]
7. [REDACTED]
8. Are willing and able to follow instructions and can be present for the required study visits for the duration of the study.
9. Have verbal communication skills adequate to participate.

Specular microscopy subset subjects only:

10. Have a central corneal endothelial cell density [REDACTED]

4.2 *Subject exclusion criteria*

Subjects who meet any of the following exclusion criteria are ineligible for this study:

1. Have participated in an investigational study (drug or device) within the past 30 days.
2. [REDACTED]
3. [REDACTED]
4. [REDACTED]
5. Have ocular surface disease requiring punctal plugs.
6. Have evidence of any current ocular inflammation.
7. Subject who must wear contact lenses on study visit days.
8. Current ocular allergy symptoms.
9. Any condition, including alcohol or drug dependency, that would limit the subject's ability to comply with the procedures of the protocol (per Investigator's judgment).
10. [REDACTED]

11. The subject or a close relative of the subject is the investigator or a sub-investigator, research assistant, pharmacist, study coordinator, or other staff directly involved in the conduct of the study.

12. [REDACTED]

13. Previous participation in a clinical study of AG-920.

14. [REDACTED]

4.3 Subject replacement

Discontinued subjects may be replaced by enrollment of additional subjects until approximately 240 evaluable subjects have completed the study.

5 TREATMENT OF SUBJECTS

Subjects will receive a single dose of IMP (2 drops 30 seconds apart) in one (study) eye. The IMP will be randomized as either AG-920 or Placebo. The study eye will be randomized as either right eye (OD) or left eye (OS). The dose will be administered by the clinic staff.

5.1 Concomitant medications

5.1.1 Prohibited medications

The list of prohibited medications provided below may not be comprehensive. Investigators are encouraged to consult with the Medical Monitor for a decision about proceeding if they have any questions or concerns about any medication.

The following medications are prohibited.

• [REDACTED]

As noted in the exclusion criteria (Section 4.2), individuals must refrain from contact lens wear on the Dosing Day.

5.1.2 Allowed medications

Other than the agents and/or times noted above, systemic therapy with agents is allowed.

Use of all medications should be documented on the appropriate CRF. Investigators are encouraged to contact the Sponsor for any questions regarding allowed medications. Judgment of continued study participation by the subject, and inclusion of this subject's subsequent visits in the safety and efficacy analysis will be made by the Medical Monitor.

All medications which the subject has taken within 30 days prior to screening and during the study will be recorded in the CRF. The name of the drug, dose, route of administration, duration of treatment and indication will be recorded for each medication. For combination products (e.g., Contac®), the brand name is required. For non-combination products, the generic name is desired. The use of routine ophthalmic diagnostic pharmaceutical agents (e.g., fluorescein and local anesthetic) will be allowed, and individual documentation not required.

5.2 Female Subjects

Female subjects of childbearing potential must not be pregnant or breastfeeding at Randomization. These subjects must have a negative urine pregnancy test at Screening in order to be eligible for the study.

Female subjects who are not of childbearing potential must meet at least one of the following criteria:

- At least 1 year since the last menstrual period
- Surgically sterile (tubal ligation, bilateral oophorectomy, salpingectomy, or hysterectomy)
- Congenitally sterile
- Diagnosed as infertile and not undergoing treatment to reverse infertility

6 STUDY PROCEDURES

6.1 General Procedures:

The study will consist of 1 or 2 clinic visits and 1 Follow-up Phone Call. There will be a subset of subjects (~18 at one site) who will participate in specular microscopy (Visit 3). These subjects only will have one additional visit 90 days following Visit 2.

All ocular assessments will be performed on both eyes. Subjects will be screened for entry (Visit 1) and randomized/treated at (Visit 2). Visit 1 and 2 may be on the same day. At randomization, subjects will receive IMP (2 drops 30 seconds apart) in the study eye. Subjects will then have a safety Follow-up Phone Call 1-4 days (Days 2-5) following Visit 2. Subjects participating in specular microscopy will have one additional visit on Day 90 (Visit 3).

6.2 Re-screening Procedures:

A subject who is first designated as a screen failure prior to being randomized will be allowed to rescreen one additional time 7-30 days later.

6.3 Visit 1 (Screening) – Day -2 to 0/1

Visit 1 may be combined with Visit 2 in order to accommodate clinic logistics. If both visits are combined, Visit 1 will last anywhere from 1-3 hours. If topical anesthetic drops are used to assess IOP, subject must wait at least 1 hour before IMP treatment. Topical anesthetic drops may cause a mild stinging or burning sensation upon instillation.

6.4 Visit 2 (Randomization/Treatment) – Day 1

Visit 2 must occur within 3 days of Visit 1 (Screening) if it is not performed on the same day as Visit 1. As noted in Section 6.3, Visit 1 and Visit 2 may be performed on the same day for clinic logistics. If a topical anesthetic is used to measure IOP at Screening (Visit 1), there must be at least a 1-hour interval post-anesthetic drops prior to treatment with IMP. At Visit 2, subjects are expected to be in the clinic for 60 to 90 minutes post dose.

6.4.3

6.5 Follow-Up Phone Call (Day 2-5)

Subjects will receive a phone call from site staff between Days 2-5, which is 1-4 days (24-96 hours post-dose) following treatment with IMP. Subjects will be asked about

- Assess for AEs
- Collect any changes to concomitant medications
- If they are in the specular microscopy group, they will be reminded of their visit at Day 90 (Visit 3) and appointment confirmed.

If there are any ongoing adverse events, the subject will be instructed to return to the investigator's office for appropriate evaluation. If there are no ongoing adverse events, the subject will be considered completed.

For subjects NOT in the specular microscopy subset, subjects will be thanked for their participation and released to follow their normal standard of care.

6.6 Visit 3 - Specular microscopy (90 days) – subset of subjects ONLY

For subjects in the specular microscopy subset, 90 days \pm 5 days after Visit 2, these subjects will return to the study site for the following assessments:

- Perform of specular microscopy in both eyes.
- Assess for AEs
- Collect any changes to concomitant medications

If there are any ongoing adverse events, the subject will be instructed to return to the investigator's office for appropriate evaluation. If there are no ongoing adverse events, the subject will be considered completed.

Subjects will be thanked for their participation and released to follow their normal standard of care.

6.7 *Unscheduled visits*

To ensure subject safety during the trial, any subject who requires additional follow-up during the study for any reason (that does not fall on a scheduled study visit) should have that visit recorded as an Unscheduled Visit.

6.8 *COVID-19 Pandemic Accommodations*

This study may be conducted during the COVID-19 pandemic. As a result, American Genomics is providing guidance to Investigators on how to modify the current protocol based on [guidance documents from the FDA](#) and other regulatory authorities. The objective of these potential modifications is to ensure the safety of trial participants and clinic staff, maintain compliance with good clinical practice (GCP), and minimize the risks to trial integrity during the COVID-19 pandemic.

To ensure the safety of trial participants and to minimize or eliminate hazards as a result of the COVID-19 pandemic, the following alternative processes and procedures may be implemented when necessary:

1. Depending on local COVID-19 prevalence and prevailing local ordinances and guidances, some screening visit procedures may be conducted by telephone, by video conferencing, or by remote staff in the subject's home.
2. The Randomization/Treatment Visits cannot be done by telephone or video conferencing and must be completed at the investigative site, if it is safe and feasible, per Investigator's judgment.
3. Site specific accommodations should be implemented per state and local guidances possibly including social distancing or personal protective equipment (PPE) requirements.
4. Remote monitoring visits of clinical trial data may be implemented.

7 ASSESSMENT OF EFFICACY

The is no measure of efficacy in this study.

8 ASSESSMENT OF SAFETY

8.1 *Specification of safety parameters*

The assessment of safety and tolerability will be evaluated changes in by:

- BCVA (ETDRS)
- Intraocular pressure
- Biomicroscopy and external eye exam of anterior segment including evaluation of cornea, conjunctiva and anterior chamber.
- Heart rate and Blood pressure
- AEs (post treatment)
- AEs will be collected at every visit. See Section 8.3 for details on collection and reporting of AEs.
- (Subset only) Specular microscopy for assessment of corneal health.

Screening only:

- Urine pregnancy test for females of childbearing potential

8.2 The methods and timing for assessing, recording, and analyzing safety parameters

Methods may be found in Table 1 and Appendix 1.

8.3 Adverse events¹

All AEs occurring after the first dose of IMP and throughout the remainder of the study period (Follow-up Phone Call; Visit 3 for subjects participating in specular microscopy) will be considered TEAEs and must be documented on the relevant Electronic Data Capture (EDC) pages and in the source documents. Whenever possible, the diagnosis, if available, and not the symptoms should be reported as the AE. AEs and Serious Adverse Events (SAEs) will be coded according to the Medical Dictionary for Regulatory Activities (MedDRA).

Documentation of adverse events/adverse reactions includes start date and stop date, severity, action(s) taken, seriousness and outcome.

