IEC	Independent Ethics Committee
IMP	Investigational Medical Product
IOP	Intraocular pressure
IRB	Institutional Review Board
ITT	Intent-to-Treat
logMAR	Logarithmic Minimum Angle of Resolution
MedDRA	Medical Dictionary for Regulatory Activities
NSAID	Non-steroidal anti-inflammatory drug
OD	Oculus dexter (Right eye)
OTC	Over the Counter
OS	Oculus sinister (Left eye)
PP	Per protocol
PPE	Personal protective equipment
PT	Preferred Term
SAE	Serious adverse event
SAP	Statistical Analysis Plan
SOC	System/Order/Class
SOP	Standard Operating Procedures
TEAE	Treatment emergent adverse event
UPT	Urine Pregnancy Test
US	United States
VA	Visual acuity

Summary

Study Number	AG-920-CS303	
Clinical Phase:	Phase 3	
Type of study	Safety	
Name of Investigational product:	Articaine Sterile Topical Ophthalmic Solution (AG-920)	
Duration of treatment per subject	1 day	
Objectives and Endpoints:	Primary Objective To evaluate the ocular safety of a single topical ocular administration of Articaine Sterile Topical Ophthalmic Solution (2 drops 30 seconds apart)	Primary Endpoints Visual acuity, intraocular pressure, biomicroscopy, AEs, TEAEs, SAEs, withdrawals due to TEAEs
	Secondary Objectives A subset of up to 20 subjects (with expectations that 12 receiving AG-920 and 6 receiving vehicle) will undergo specular microscopy prior to and 3 months after receiving masked study medication to evaluate the effect of AG-920 on corneal endothelial cell count (ECC).	Secondary Endpoints Mean change from baseline in corneal endothelial cell density after treatment with AG-920
Subject Population:	Healthy volunteers Exclusion criteria may be found in Section 4.2.	
Design:	Randomized, placebo (vehicle) controlled, double-masked, parallel-group. Unequal randomization (2:1 Active:Placebo)	
Visit Schedule:	Study visits will consist of: 
 • a 1-3 day Screening Period • a dosing visit (multiple timepoints over 90 minutes) • a follow-up phone call 1-4 days following dosing And 
 • a follow-up visit at 90-95 days following dosing (ONLY for the subset of subjects participating in the ECC evaluation) 	
Number of Investigational Sites:	Up to 5 US sites	
Estimated Total Sample Size:	240 total evaluable subjects; 160 AG-920; 80 Placebo.	

	A subset of up to 20 of subjects will have specular microscopy performed.

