2 OBJECTIVES AND ENDPOINTS

Primary Objective	Primary Endpoints
To evaluate the ocular safety of a single dose of AG-920 after topical ocular administration of Articaine Sterile Topical Ophthalmic Solution (2 drops 30 seconds apart)	Visual acuity, intraocular pressure, biomicroscopy, AEs, TEAEs, SAEs, withdrawals due to TEAEs
Secondary Objectives	Secondary Endpoints
A subset of up to 20 subjects (with expectations that 12 receiving AG-920 and 6 receiving vehicle) will undergo specular microscopy prior to and 3 months after receiving masked study medication to evaluate the effect of AG-920 on corneal endothelial cell count (ECC).	Mean change from baseline in corneal endothelial cell density after treatment with AG-920

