9.4.8 Adverse Events

Verbatim descriptions of AEs will be mapped to MedDRA thesaurus terms and be presented in a data listing. Treatment emergent AEs, those that occur after the first dose of study medication, will be summarized by treatment group using frequency counts and percentages for each system organ class (SOC) and preferred term (PT) within each SOC. Summaries will be presented separately for ocular and non-ocular AEs. These summaries will also be presented by the relationship to the Investigational Medical Product (related, unrelated) and by severity of the AE (mild, moderate, severe). Fisher's exact test will be used to test the difference in proportions of subjects with each AE between treatment groups (SOC and PT).

9.5 *Procedure for accounting for missing, unused, or spurious data*

For this safety study, only observed data will be used. This is no planned method for imputation of missing data.

9.6 *Procedure for reporting deviations from the statistical plan*

Any deviations from the statistical plan will be described and a justification given in the final statistical report.

9.7 *Data listings*

Data listings will be prepared for all data on the database.

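### Late adverse events are pooled over about 1-4 days of follow-up for most subjects and about 90 days for the specular-microscopy subset, with no visible table on the subset's own denominator

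*Protocol*

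**What the plan says.** **Window in the protocol.** Protocol 8.3 states that events after the first dose and "throughout the remainder of the study period (Follow-up Phone Call; Visit 3 for subjects participating in specular microscopy) will be considered TEAEs". For subjects outside the subset the last scheduled AE contact is the call in Protocol 6.5: "Subjects will receive a phone call from site staff between Days 2-5, which is 1-4 days (24-96 hours post-dose) following treatment with IMP".

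**The subset.** Protocol 2 states: "A subset of up to 20 subjects (with expectations that 12 receiving AG-920 and 6 receiving vehicle) will undergo specular microscopy". Protocol 3.4 gives up to 18, and Protocol 6.1 gives about 18 at one site. Visit 3 is at 90 ± 5 days in Protocol 3.6.1 and 6.6, while the Summary has "a follow-up visit at 90-95 days following dosing". AEs are actively assessed at Visit 3 (Protocol 6.6), in line with Protocol 8.1: "AEs will be collected at every visit".

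**Summary measure.** Under Protocol 9.4.8, TEAEs "will be summarized by treatment group using frequency counts and percentages for each system organ class (SOC) and preferred term (PT) within each SOC". They are also presented separately for ocular and non-ocular events, by relationship and by severity, and Fisher's exact test compares the arms for each SOC and PT. Nothing in that section separates the subset or adjusts for length of follow-up.

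**The SAP.** SAP 2.9.3 defines TEAEs differently: onset from the start of treatment to the end of the dosing day, for every subject. Later events are post-treatment AEs, for which SAP section 7 lists Table 4.2.4. SAP 5.3 nevertheless divides TEAEs into on-treatment-day and off-treatment-day onset in Tables 4.3.1-4.3.3, which does not fit the SAP's own dosing-day definition.

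**The concern.** A percentage of subjects with an event is easy to interpret only when subjects are watched for similar lengths of time. Here a small group from one site is watched more than 20 times as long as the rest. For late events the pooled percentage estimates neither the risk over the first few days nor the risk over 90 days. It is a mixture whose value depends on how many subset subjects happen to be in the denominator.

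This matters because AEs, TEAEs, SAEs and withdrawals due to TEAEs are among the primary endpoints of a single-dose safety study. Three months of ordinary illness in 18-20 people can raise the reported frequency of events after a one-day treatment, and one site's reporting habits would weigh heavily on the late events. Choosing one document's TEAE definition over the other does not remove the mixing. It only decides which table carries it.

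**Working it through.** The plan gives no observation-time figure to reproduce. Its 240 subjects (160 and 80) are set by required safety exposure (Protocol 9.2, SAP 2.5), not by a power calculation.

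**Inputs**
- N = 240, 160 AG-920 and 80 placebo (Protocol Summary).
- Subset n = 18 or 20, expected split 12:6 (Protocol Summary, 2 and 3.4; SAP 1.1).
- Subset follow-up T = 90 days, range 85-95 (Protocol 3.6.1, 6.6).
- Other subjects' follow-up d = 1 to 4 days (Protocol 6.5); 2.5 is the midpoint.

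**1. Share of AE observation time supplied by the subset** = nT / [nT + (240 − n)d]

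| n | nT (T = 90) | (240 − n)d, d = 1 to 4 | Share |
|---|---|---|---|
| 18 | 1,620 | 222 to 888 | 87.9% to 64.6% |
| 20 | 1,800 | 220 to 880 | 89.1% to 67.2% |

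Over T = 85-95 days as well, the range is 63.3% to 89.6%. The subset is 18/240 = 7.5% of subjects (20/240 = 8.3%).

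Table 4.2.4 drops the dosing day. Taking that as one day off everyone, with the call at day 4, the share is (18 × 89) / (18 × 89 + 222 × 3) = 1,602/2,268 = 70.6%. The mixing there is no smaller.

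**2. Effect on the reported percentage.** The plan counts subjects with an event, so person-time alone is not the answer. Assume a constant background AE risk r per 30 days. This is not in the documents and is shown as a range. Subset risk = 1 − (1 − r)^(90/30). Other subjects' risk = 1 − (1 − r)^(2.5/30).

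| r | Subset, events in 18 | Others, events in 222 | Pooled % of 240 | % on short window | Difference |
|---|---|---|---|---|---|
| 5% | 2.6 | 0.9 | 1.5 | 0.4 | 1.0 points |
| 10% | 4.9 | 1.9 | 2.8 | 0.9 | 2.0 points |
| 20% | 8.8 | 4.1 | 5.4 | 1.8 | 3.5 points |

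Moving the call to day 1 or day 4 changes the differences by no more than 0.1 point. With n = 20 they are 1.2, 2.2 and 3.9 points.

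**3. Comparison of arms.** With k of 18 subset subjects on AG-920, mean follow-up is [90k + 2.5(160 − k)]/160 on AG-920 and [90(18 − k) + 2.5(62 + k)]/80 on placebo. The last column uses r = 10%.

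| Split | Mean days, AG-920 vs placebo | Background AE % |
|---|---|---|
| 12:6 | 9.1 vs 9.1 | 2.8 vs 2.8 |
| 14:4 | 10.2 vs 6.9 | 3.2 vs 2.2 |
| 10:8 | 8.0 vs 11.3 | 2.5 vs 3.5 |

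At the expected split there is no imbalance, because 12/160 = 6/80 = 7.5%. If the subset were an unrestricted draw of 18 from 240, a split with 10 or fewer, or 14 or more, on AG-920 would have hypergeometric probability 0.215 + 0.221 = 0.436. The randomization details are redacted, so whether that draw applies cannot be checked.

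**4. SAEs.** Protocol 8.3.3 extends SAE reporting to four weeks after the last administration for everyone. Counting the other 222 subjects to 28 days, the subset's share is 1,620 / (1,620 + 222 × 28) = 1,620/7,836 = 20.7%, not 65-88%.

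**The case against.** Three stronger conclusions are tempting, and the documents do not support them.

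**That no planned table uses a window shared by all subjects.** SAP 2.9.3 gives every subject the same dosing-day TEAE window, and Protocol 9.4.1 leaves the fuller methods to the SAP. Even under the protocol definition, the on-treatment-day part of Tables 4.3.1-4.3.3 is a shared window. What stands is narrower. Late events are pooled under either definition, and no listed table title puts them on the subset's denominator. The table shells are not in the public text, so a split there cannot be excluded.

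**That the ocular safety result itself is seriously distorted, because the subset supplies 65-88% of observation time.** Most of the time is not most of the events. Protocol 1.2 expects reactions on instillation, when all treated subjects are under observation. Protocol 9.4.8 separates ocular from non-ocular events and related from unrelated ones, and SAP Tables 4.2.5 and 4.2.6 separate the eyes. Most unrelated illness would fall in the non-ocular, unrelated rows. SAEs have the four-week reporting window. This objection stands and limits the point to late and background events.

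**That the arm comparison is confounded by follow-up time.** At 12:6 it is not. A departure of two subjects either way shifts background incidence by about 1 point between arms at the 10% assumption, and the visible text neither establishes nor rules out control of the split.

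It can also be argued that counting every on-study event as a TEAE is a legitimate choice. It is, but it does not answer how to read a single percentage built on two very different follow-up lengths.

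**Conclusion.** The concern holds in limited form. Protocol 8.3 and 9.4.8 together pool events from two follow-up lengths in one percentage per arm. The SAP's definition moves the problem to Table 4.2.4 rather than removing it. The distortion is in the level and meaning of late-event percentages: roughly 1-4 points on the any-AE figure, if background risk is constant at 5-20% per 30 days (assumed). The finding that the subset supplies more than half of the scheduled AE observation time needs no such assumption. It holds at every subset size, visit window and call time the documents give. Acute instillation reactions are little affected. Bias between arms is conditional on a subset split away from 2:1 and cannot be judged from the redacted scheme.

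**What to change.** Make the change when the protocol and SAP TEAE definitions are reconciled, before unmasking:

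1. Base the main AE incidence tables and the Fisher tests on onset from the first drop to the follow-up call (Day 2-5). State that this window still varies with call timing, from 24 to 96 hours.
2. Split Table 4.2.4 at the call. Report AEs with onset after the call and up to Visit 3 by arm, using as denominator the subset subjects followed beyond the call. The SM population in SAP 3.1 is not quite that group, since one specular-microscopy visit, which may be Screening, is enough to enter it.
3. Keep SAEs from any subject in the SAE table, listings and narratives. This includes SAEs outside the subset reported after the call but within the four weeks of Protocol 8.3.3, which would otherwise fit neither the main tables nor the subset table. The scope and title of Table 4.4.3, now limited to treatment-emergent SAEs, need to match.

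The cost is one split table and SAP wording, with no new data or visits. Editing Protocol 8.3 or 9.4.8 also needs an approved amendment under Protocol 12.4. The drawback is that late subset events leave the headline tables, but they stay visible in their own table and in the listings.
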